## **7.4        INTERIM ANALYSES**

No formal interim analysis is planned. A preliminary analysis of PK parameters and safety may be performed, if requested by the Clinical Trial Leader, the investigator, or Trial Clinical Pharmacokinetics.

## **7.5        HANDLING OF MISSING DATA**

### **7.5.1        Safety**

It is not planned to impute missing values for safety parameters.

### **7.5.2        Pharmacokinetics**

Handling of missing PK data will be performed according to the relevant Corporate Procedure (current version).

PK parameters that cannot be reasonably calculated based on the available drug concentration-time data will not be imputed.

## **7.6        RANDOMISATION**

This is a randomized trial. Consecutive subject numbers will be assigned via the eDC system. Subjects will be randomized within each matched pair in a 1:1 ratio (IV to SC).

The sponsor will arrange for the randomization as well as packaging and labelling of trial medication. The randomization list will be generated using a validated system that uses a pseudo-random number generator and a supplied seed number so that the resulting allocation is both reproducible and non-predictable.

The randomization list will contain additional blocks to allow for subject replacement (refer to Section [3.3.5](#)).

## **7.7        DETERMINATION OF SAMPLE SIZE**

It is planned to enter a total of 28 subjects in the trial, because this sample size is considered sufficient to achieve the aims of this exploratory trial. With this sample size, the following precision in estimating the ratio of geometric means (test/reference) can be expected with 95% probability. Precision is defined as the ratio of upper CI limit to the relative BA estimate. Note that the precision is independent of the actual ratio of geometric means.

The observed geometric coefficient of variation (gCV) for BI 765080 in the 1450-0001 trial [[c31414158](#)] was roughly 14% for  $C_{max}$  and 25% for AUC.

Proprietary confidential information © 2021 Boehringer Ingelheim International GmbH or one or more of its affiliated companies

For various assumptions around the gCV of 25%, Table [7.7: 1](#) provides an overview of the achievable precision for estimating the ratio of geometric means (test/reference). For illustrative purposes, the expected 90% confidence intervals are displayed for different values of the ratios T/R of geometric means.

Table 7.7: 1

Precision that can be expected with 95% probability and illustrative two-sided 90% confidence intervals around the ratios of geometric means (T/R) for different gCVs in a matched pair parallel trial (N=28)

gCV [%]	Precision upper CL / relative BA estimate	Ratio [%]*	Lower CL [%]	Upper CL [%]
22.5	1.13	25	22.10	28.28
22.5	1.13	60	53.04	67.87
22.5	1.13	90	79.56	101.81
25.0	1.15	25	21.81	28.66
25.0	1.15	60	52.34	68.78
25.0	1.15	90	78.51	103.18
27.5	1.16	25	21.52	29.04
27.5	1.16	60	51.65	69.70
27.5	1.16	90	77.48	104.55

\*Ratio of geometric means (test/reference) for a PK endpoint is defined by  $\exp(\mu_T)/\exp(\mu_R)$ .

The expected 90% confidence interval limits in the table were derived by

$$CI\ limit_{upper,lower} = \exp(\ln(\theta) \pm \omega),$$

with  $\theta$  being the ratio (T/R) on original scale and  $\omega$  the distance from the estimate  $\theta$  to either confidence interval limit on the log-scale, which was obtained from the achievable precision on the original scale.

The calculation was performed as described by Julius [\[R11-5230\]](#) using R Version 4.0.1.

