#### FIH-Study (Trial 1450-0001)

The FIH (first-in-human) trial [[c31414158](#)] is ongoing and explored safety, tolerability, pharmacokinetics, and pharmacodynamics of intravenously administered BI 765080 in healthy male subjects. Subjects received single ascending IV doses of 1 mg up to 200 mg BI 765080 or placebo. Overall, the study included 48 male subjects with 36 subjects treated with BI 765080 and 12 subjects treated with placebo.

At preferred term level, all the reported treatment-emergent AEs are shown below:

Proprietary confidential information © 2021 Boehringer Ingelheim International GmbH or one or more of its affiliated companies

headache (BI 765080: 3/38 subjects [8.3 %]; placebo: 1/12 subjects [8.3%]), upper respiratory tract infection (BI 765080: 2/36 subjects [5.6 %]; placebo: 0), post vaccine reactogenicity (BI 765080: 1/36 subjects [2.8 %]; placebo: 0), headache post vaccine Covid-19 (BI 765080: 1/36 subjects [2.8 %]; placebo: 0), vomiting (BI 765080: 1/36 subjects [2.8 %]; placebo: 0), vision blurred (BI 765080: 1/36 subjects [2.8 %]; placebo: 0), back pain (BI 765080: 1/36 subjects [2.8 %]; placebo: 0), bronchitis (BI 765080: 1/36 subjects [2.8 %]; placebo: 0), tooth abscess (BI 765080: 1/36 subjects [2.8 %]; placebo: 0), myalgia right upper leg (BI 765080: 1/36 subjects [2.8 %]; placebo: 0), throat irritation (BI 765080: 0; placebo: 1/12 subjects [8.3 %]), weight increased (BI 765080: 0; placebo: 1/12 subjects [8.3 %]), herpes zoster reactivation (BI 765080: 0; placebo: 1/12 subjects [8.3 %]),

All of treatment-emergent AEs were assessed as not drug-related. There were six AEs of moderate intensity (four AEs with BI 765080 and two AEs with placebo). Four moderate AEs with BI 765080 included tooth abscess, headache post vaccine Covid-19 and upper respiratory infection in two subjects. Two moderate AEs with placebo included headache and herpes zoster reactivation. All remaining AEs were of mild intensity.

There were no relevant changes compared to placebo for laboratory safety, including clinical chemistry, hematology, coagulation parameters, and urinalysis. Deaths, serious AEs, and protocol-specified AEs of special interest were not reported in this trial. No clinically relevant changes were observed in 12 lead ECGs, vital signs, and physical examinations. In addition, no adverse event related to local tolerability was reported.

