#### **3.3 SELECTION OF TRIAL POPULATION**

It is planned that 28 healthy male subjects (14 subjects with IV and 14 subjects with SC) will enter the study to have at least 12 evaluable subjects available in each group. They will be recruited from the volunteers' pool of the trial site.

Participants in SC and IV groups will be matched for age (18-36 or 37-55 years at screening) and body weight ( $\pm 10\%$  inclusive). That means, that the 2 subjects of one matched pair are either 18-36 years (inclusive) or 37-55 years old (inclusive) and that the difference of their body weight does not exceed 10% (e.g. 80 kg and 88 kg).

Only Caucasian male subjects will be included in the study.

A log of all subjects enrolled into the trial (i.e. who have signed informed consent) will be maintained in the ISF irrespective of whether they have been treated with investigational drug or not.

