#### **7.3.1 Primary endpoint analyses**

##### Primary analyses

The statistical model used for the analysis of the primary endpoints will be an analysis of variance (ANOVA) model on the logarithmic scale. That is, the PK endpoints will be log-transformed (natural logarithm) prior to fitting the ANOVA model. This model will include effects accounting for the following source of variation: treatment and matching pair. The effect of treatment will be considered as fixed. For each matched pair in the study a pair number will be assigned for analysis purpose. The resulting variable 'matched pair' will be considered as random effect. The model is described by the following equation:

$$y_{km} = \mu + \tau_k + s_m + e_{km}, \text{ where}$$

$y_{km}$  = logarithm of response measured on subject m receiving treatment k,

Proprietary confidential information © 2021 Boehringer Ingelheim International GmbH or one or more of its affiliated companies

$\mu$  = the overall mean,

$\tau_k$  = the  $k^{\text{th}}$  treatment effect,  $k = 1, 2,$

$s_m$  = the effect associated with the  $m^{\text{th}}$  matching pair,  $m = 1, 2, \dots, 14,$

$e_{km}$  = the random error associated with the  $m^{\text{th}}$  subject who received treatment  $k.$

where  $s_m \sim N(0, \sigma_B^2)$  i.i.d.,  $e_{km} \sim N(0, \sigma_W^2)$  i.i.d.,  $\sigma_W^2$  and  $s_m, e_{km}$  are independent random variables.

Point estimates for the ratios of the geometric means (test/reference) for the primary endpoints (see Section 2.1) and their two-sided 90% confidence intervals (CIs) will be provided.

For each endpoint, the difference between the expected means for  $\log(T)-\log(R)$  will be estimated by the difference in the corresponding adjusted means (Least Squares Means). Additionally their two-sided 90% confidence intervals will be calculated based on the residual error from the ANOVA and quantiles from the t-distribution. These quantities will then be back-transformed to the original scale to provide the point estimate and 90% CIs for each endpoint.

In addition to the model based approach all parameters will be calculated and analysed descriptively.

[figure not shown]

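### Table 7.7:1 states too favourable a precision: its values reproduce only with 28 pairs although 14 are planned, and its narrow gCV band rests on the 100 mg IV group alone

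*Protocol*

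**What the plan says.** Protocol Section 7.7: "It is planned to enter a total of 28 subjects in the trial". The justification is the precision of the geometric mean ratio that should be reached with 95% probability. The section cites gCVs from trial 1450-0001 of roughly 14% for Cmax and 25% for AUC. It then tabulates precision "For various assumptions around the gCV of 25" per cent:

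- gCV 22.5%: 1.13
- gCV 25.0%: 1.15
- gCV 27.5%: 1.16

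Each row is illustrated at T/R 25, 60 and 90%. At gCV 25% and T/R 60% the 90% interval is 52.34 to 68.78%.

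The design is "14 subjects with IV and 14 subjects with SC" (Section 3.3), randomised 1:1 within matched pairs (Section 7.6). The model in Section 7.3.1 indexes pairs from 1 to 14, and its intervals are "calculated based on the residual error from the ANOVA and quantiles from the t-distribution". SAP Section 7.4.1 repeats this model.

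The source of the gCV is Protocol Section 1.2.3: "Overall, the study included 48 male subjects with 36 subjects treated with BI 765080", over six IV doses. In Table 1.2.3:1 the AUC0-tz gCV from 1 to 200 mg is 50.4, 24.9, 31.3, 39.5, 25.4 and 16.0%. The same section reports target-mediated disposition that may be close to saturation at 100 mg.

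**The concern.** The cited 14% and 25% match only the 100 mg IV column (13.7% for Cmax; 25.4% and 25.2% for the two AUCs). Section 7.7 attributes them to the trial as a whole. A band of 2.5 points either side is narrow for an estimate from about 6 subjects, and neighbouring dose groups showed higher values. Because disposition depends on exposure, an SC arm with incomplete bioavailability would sit at lower exposure than 100 mg IV, where variability may be higher. The documents give no SC variability estimate.

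The table is also labelled N=28 for a matched-pair trial, so it matters whether 28 was used as a number of subjects or of pairs.

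Estimation is the stated aim (Section 7.2), and this table is the only quantitative support for the sample size. If it is too favourable, readers expect narrower intervals than the design is likely to give.

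**Working it through.** **Formula.** σ = √ln(1 + gCV²). With n pairs and n − 1 degrees of freedom, ω = t(0.95, n−1) × σ × √(2/n) × √[χ²(0.95, n−1)/(n−1)]. Precision = exp(ω), and the limits are ratio × exp(±ω).

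**Step 1: reproduce the table.** With n = 28 (df 27) the multiplier of σ is 1.703 × 0.2673 × 1.2189 = 0.5549. At gCV 25%, σ = 0.2462 and ω = 0.1366, so precision is 1.146 and the limits at T/R 60% are 52.34 and 68.78%. All 18 tabulated limits agree to two decimals. With 14 pairs (df 13) the result is 1.241. An unmatched comparison of 14 per arm (df 26) gives 1.214. Neither reproduces the table.

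**Step 2: correct the pair count only.** With n = 14 (df 13) the multiplier is 1.771 × 0.3780 × 1.3115 = 0.8779. Precision at gCV 22.5, 25 and 27.5% is 1.215, 1.241 and 1.267. At gCV 25% and T/R 60% the interval is 48.3 to 74.5%.

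**Step 3: how well is 25% known?** Assume 36/6 = 6 subjects at 100 mg (5 df). The 95% interval for a gCV of 25.4% is then about 16 to 68%. Equal-weight pooling of σ² over dose groups gives:

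- 10 to 200 mg: 28.3%
- 50 to 200 mg: 28.4%
- 10 to 100 mg: 30.7%
- 25 to 100 mg: 32.5%
- all six doses: 32.8%
- 100 and 200 mg only: 21.2%

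Only the last of these falls below the table's 27.5% ceiling.

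**Step 4: place the SC arm by exposure.** T/R is a ratio of AUCs, not of doses. Against 7.10 million h·µg/L at 100 mg IV, the 25 mg group is 0.868/7.10 = 12% and the 50 mg group is 2.50/7.10 = 35%. Linear interpolation of gCV on log AUC between neighbouring groups gives the SC-arm gCV. For example, at T/R 60% the AUC is 4.26 million and the fraction is ln(4.26/2.50)/ln(7.10/2.50) = 0.511, so gCV = 39.5 − 0.511 × 14.1 = 32.3%. The IV arm stays at 25.4% because it repeats that dose and route. The common σ² is the mean of the two arms.

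| T/R | SC AUC (million) | SC gCV | Common gCV | Precision, 28 pairs | Precision, 14 pairs |
|---|---|---|---|---|---|
| 25% | 1.78 | 36.8% | 31.6% | 1.19 | 1.31 |
| 60% | 4.26 | 32.3% | 29.0% | 1.17 | 1.28 |
| 90% | 6.39 | 26.8% | 26.1% | 1.15 | 1.25 |

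If the SC arm is set instead to the observed 31.3% or 39.5%, the common gCV is 28.5% or 33.1%, and precision on the 28-pair formula is 1.17 or 1.20.

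**Step 5: separate the two effects at T/R 60%.**

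- Stated at gCV 25%: 52.3 to 68.8%
- gCV effect alone (29.0%, 28 pairs): 51.2 to 70.3%
- Pair count alone (25%, 14 pairs): 48.3 to 74.5%
- Both: 46.7 to 77.0%

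**Step 6: sensitivity rows on 14 pairs.** gCV 30, 35 and 40% give 1.294, 1.348 and 1.402.

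**The case against.** A reader might infer that the SC arm would have a gCV of 31 to 40% whatever its bioavailability, by reading T/R 25 to 60% as 25 to 60 mg IV. The documents do not support this. AUC rises more than proportionally with dose up to 100 mg, so the 25 mg group lies below every tabulated ratio. T/R 90% stays inside the tabulated range, and no expected bioavailability is given.

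A reader might also want 32.5% in both arms as the base case. That figure pools three of six groups and inflates an IV arm whose dose and route gave 25.4%. Pools that include 200 mg come to about 28%, apart from the all-dose pool (32.8%). With about 6 subjects per group, 50 and 100 mg are not clearly different (variance ratio 2.32, p about 0.38). These limits stand. The same imprecision also means the data cannot support a band as tight as 22.5 to 27.5%.

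Matching on age and weight could lower the residual variance, and the intervals use the residual. To recover 1.15 with 14 pairs at a total gCV of 25%, the within-pair correlation would have to be about 1 − (0.5549/0.8779)² = 0.60. The documents state no correlation, so this remains possible but unsupported.

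For Cmax the cited gCV is 14%, which gives 1.13 even with 14 pairs, so the point concerns AUC. Finally, the trial is exploratory, has no acceptance range and calls the intervals illustrative. That limits the consequence, but the stated precision is still wrong for the planned number of pairs.

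**Conclusion.** The stated 1.13 to 1.16 is too favourable for AUC. Most of the gap comes from the pair count: at gCV 25% it moves precision from 1.15 to 1.24. The narrow gCV band is a second, smaller weakness. Alone it moves precision to about 1.17 to 1.20, and only at low to moderate bioavailability; at T/R 90% the tabulated range is adequate.

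This rests on an equal split of the 36 treated subjects, on interpolation between small IV groups standing in for unknown SC variability, and on matching removing little variance. The reproduction with 28 pairs needs none of these.

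It would go too far to conclude that the trial is underpowered or needs more subjects. No hypothesis is tested, and what changes is the expected width of the interval.

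**What to change.** Recompute every row of Table 7.7:1 on 14 pairs with 13 degrees of freedom, including all illustrative limits: 1.22, 1.24 and 1.27 at gCV 22.5, 25 and 27.5%. Add gCV 30, 35 and 40% as sensitivity rows (1.29, 1.35 and 1.40). The existing rows must change too; otherwise the table would mix 28-pair and 14-pair values.

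State in Section 7.7 that the 25% and 14% come from the 100 mg IV group of trial 1450-0001, that no SC variability estimate is available, and that the calculation assumes matching removes little variance. Keep 25% as the central row, and do not make 32.5% in both arms the base case.

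The cost is a protocol text and table change and a less favourable stated precision. The number of subjects, the conduct of the trial and the analysis model stay as they are, and the SAP model needs no edit.

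### Table 7.7:1 gives the precision of 28 matched pairs, but the trial has 14: at gCV 25% the precision is about 1.24, not 1.15

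*Protocol*

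**What the plan says.** Protocol Section 7.7 bases the sample size on precision alone: "It is planned to enter a total of 28 subjects in the trial", and "With this sample size, the following precision in estimating the ratio of geometric means (test/reference) can be expected with 95% probability". Precision is the upper 90% confidence limit divided by the point estimate. The section cites a gCV of roughly 14% for Cmax and 25% for AUC from the first-in-human trial. Table 7.7:1 is built around 25% and is captioned as "90% confidence intervals around the ratios of geometric means (T/R) for different gCVs in a matched pair parallel trial (N=28"). It gives precision 1.13, 1.15 and 1.16 at gCV 22.5, 25 and 27.5%, with limits for ratios of 25, 60 and 90%.

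The design is fixed elsewhere. Section 3.3: "It is planned that 28 healthy male subjects (14 subjects with IV and 14 subjects with SC) will enter the study", with at least 12 evaluable per group. Section 7.6: "Subjects will be randomized within each matched pair in a 1:1 ratio (IV to SC"). Section 4.1.4: each subject receives one single dose. In Section 7.3.1, "The resulting variable 'matched pair' will be considered as random effect", the pair index runs from 1 to 14, and the intervals are "calculated based on the residual error from the ANOVA and quantiles from the t-distribution". SAP Section 7.4.1 repeats this model and index.

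**The concern.** Each subject receives one treatment, so a treatment comparison within a pair uses two subjects, and 28 subjects make 14 pairs. Yet the tabulated half-widths look too small for 14 pairs at a gCV of 25%. If the total number of subjects stands where the number of pairs belongs, the standard error is too small by a factor of sqrt(2) and the degrees of freedom are 27 instead of 13.

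The plan has no hypothesis test, no power calculation and no acceptance range. Expected interval width is therefore the only quantitative argument for 28 subjects, and this table is its only source.

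**Working it through.** **Inputs.** Two-sided 90% interval, so the 0.95 quantile of t (Sections 7.2 and 7.3.1). Assurance 95%, so the 0.95 quantile of chi-square (Section 7.7). gCV 22.5, 25 and 27.5% (Table 7.7:1). Number of pairs n, with n − 1 residual degrees of freedom from a model with treatment and pair.

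**Formula.** With σ = sqrt(ln(1 + gCV²)), the log-scale half-width is

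ω = t(0.95, n−1) × σ × sqrt(2/n) × sqrt(χ²(0.95, n−1)/(n−1)).

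Precision is exp(ω), and the limits are ratio × exp(±ω). At gCV 25%, σ = sqrt(ln 1.0625) = 0.2462.

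**Reproducing the printed table.** The printed upper limit for ratio 25% at gCV 25% implies ω = ln(28.66/25) = 0.1366. With n = 28:

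ω = 1.7033 × 0.2462 × sqrt(2/28) × sqrt(40.11/27) = 0.1366, exp(ω) = 1.146.

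The other two gCVs give ω = 0.1233 and 0.1498. All 18 printed limits agree to two decimals. A 28-subject crossover with 26 degrees of freedom comes close but misses (28.68 against the printed 28.66).

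**The planned design.** With n = 14:

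ω = 1.7709 × 0.2462 × sqrt(2/14) × sqrt(22.36/13) = 0.2162, exp(ω) = 1.241.

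The ratio of half-widths is 0.2162/0.1366 = 1.58, the same at every gCV.

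| gCV | Stated precision | 14 pairs | Ratio 60%: stated | Ratio 60%: 14 pairs |
|---|---|---|---|---|
| 22.5% | 1.13 | 1.22 | 53.04–67.87 | 49.37–72.93 |
| 25.0% | 1.15 | 1.24 | 52.34–68.78 | 48.34–74.48 |
| 27.5% | 1.16 | 1.27 | 51.65–69.70 | 47.34–76.05 |

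**Other readings of 14 per arm at gCV 25%.**
- Unpaired analysis, 14 + 14, 26 degrees of freedom, 95% assurance: ω = 0.1941, precision 1.21.
- 14 pairs without the assurance factor: ω = 0.1648, precision 1.18.

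Neither gives 1.15.

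**Chance of reaching the stated precision with 14 pairs.** The half-width is at most 0.1366 when a chi-square variable with 13 degrees of freedom is at most 13 × (0.1366/0.1648)² = 8.93. That probability is 0.22.

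**Correlation needed to restore 1.15.** Matching scales σ by sqrt(1 − ρ), so ρ = 1 − (0.1366/0.2162)² = 0.60.

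**Attrition at gCV 25%.** With 12 complete pairs (11 degrees of freedom) the precision is 1.27. With 10, which is what two dropouts per arm in different pairs would leave, it is 1.32.

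**The case against.** The strongest objection is that 1.24 assumes no gain from matching. The 25% is a between-subject gCV, while the analysis interval uses the residual after pair effects are removed, and Section 3.2 says matching is meant to reduce confounding. At 14 pairs and gCV 25%, a within-pair correlation of 0.2, 0.3 or 0.5 gives precision 1.21, 1.20 or 1.17, and the chance of reaching the stated value rises to 40, 53 or 84%. So the 22%, and the statement that the interval will usually be wider than stated, belong to zero or low correlation. This stands as a condition on the corrected figure, but it does not rescue the table. The plan gives no correlation, the table itself uses the gCV as the residual, and matching on two broad age bands and weight within 10% is no evidence for 0.60.

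A second objection is that the cause is inferred. Because 2/28 = 1/14, the same limits would arise from 14 pairs with standard error σ/sqrt(14) and 27 degrees of freedom. That reading needs the gCV to describe within-pair differences, which the protocol does not say, and 14 pairs do not give 27 degrees of freedom. With the correct 13 it yields 1.17, so the printed 1.15 fails there too.

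Third, the trial is exploratory, has no acceptance range, and will report intervals from observed residual error, so the table cannot bias the result. That is correct and limits the consequence to the planning claim. Likewise, Cmax at gCV 14% has precision 1.13 with 14 pairs, so the shortfall concerns AUC. Finally, the attrition figures count complete pairs only. Replacement is allowed, and a random pair effect can use some information from an unpaired subject, so they are on the cautious side.

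**Conclusion.** The concern holds. Table 7.7:1 describes 28 pairs, and the protocol and SAP describe 14. On the table's own convention, with the gCV as the residual gCV, the precision expected with 95% probability is 1.22, 1.24 and 1.27 instead of 1.13, 1.15 and 1.16, and all nine illustrative intervals are too narrow. If matching removes part of the variance the gap shrinks, but it closes only at a within-pair correlation of about 0.60. The statement of 95% probability is therefore wrong as written. The estimator, the analysis model and the reported interval are unaffected.

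**What to change.** Recompute Table 7.7:1 with 14 pairs and 13 degrees of freedom:

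| gCV | Precision | Ratio 25% | Ratio 60% | Ratio 90% |
|---|---|---|---|---|
| 22.5% | 1.22 | 20.57–30.39 | 49.37–72.93 | 74.05–109.39 |
| 25.0% | 1.24 | 20.14–31.03 | 48.34–74.48 | 72.51–111.72 |
| 27.5% | 1.27 | 19.72–31.69 | 47.34–76.05 | 71.01–114.07 |

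Add a row for 12 evaluable pairs (at gCV 25%: 1.27, with limits 19.64–31.83, 47.13–76.38 and 70.70–114.58). Caption the table with 14 pairs (28 subjects), and state that the gCV is used as the residual gCV with no reduction credited to matching. If the sponsor wants to credit matching, it should state the assumed correlation and show a range. Then restate why 28 subjects are considered sufficient, using the corrected figures.

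The cost is a text correction to one table and its caption. No extra subjects are needed, but the stated precision becomes less favourable.
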